3.1 Trial Design

This will be a multicenter, observer-blind, controlled, randomized, Phase II study.

A total of 320 subjects aged 18 to <65 years will be included in the study.

Each subject will receive one of the 2 formulations of the Purified Vero Rabies Vaccine - Serum Free (VRVg) or the Rabies Humain Diploid Cell Vaccine Imovax Rabies. Vaccination will be according to the ESSEN post-exposure schedule (i.e., a total of 5 injections [1 injection per day] administered at D0, D3, D7, D14 and D28) and human rabies immunoglobulins (HRIG) will be administered at D0. Subjects will be assigned to the VRVg-2 groups (low, medium and high dosage), VRVg-1 group, or Imovax Rabies group with a 2:2:2:1:1 allocation ratio..

3.2 Trial Plan

The trial plan is summarized in Table 3.2.

Blood sampling:

Immunogenicity will be assessed in all subjects included in the trial, before the first vaccine injection (VAC1) (D0), before VAC4 (D14), before VAC5 (D28), 14 days after VAC5 (D42) and 6 month after VAC5 (M7). The rapid fluorescent focus inhibition test (RFFIT) assay will be used for immunogenicity assessment.

All subjects will provide a total of five 5-mL blood samples to assess the immune response induced by the rabies vaccines.

Table 3.1 below outlines the schedule of blood sampling and vaccine injection.

Table 3.1: Blood Sampling and Vaccination Schedule

| | V01 | V02 | V03 | V04 | V05 | V06 | V07 | V08 |
|-----------------------|------|---------------|----------------|-----------------|----------------|----------|----------|---------|
| Visit interval | VAC1 | VAC2= VAC1+3D | VAC3 = VAC1+7D | VAC4 = VAC1+14D | VAC5= VAC1+28D | VAC5+14D | VAC5+28D | VAC5+6M |
| Vaccine injection | x | x | x | x | x | | | |
| HRIG (Imogam® Rabies) | x | | | | | | | |
| Blood sampling (5 mL) | x | | | x | x | x | | x |

Collection of safety data:

Subjects will be observed for safety for 30 minutes after each vaccination, and any adverse events (AE)/reaction occurring between each vaccination, and up to 28 days after the fifth vaccination will be recorded by the subjects in a diary card (DC).

At each visit, study staff will either check and/or collect the safety DCs provided to subjects to report safety data. A memory aid (MA) will be provided to the subjects at V07 to collect serious adverse events (SAEs) and adverse events of special interest (AESIs) up to the end of the study. The MA will be checked and collected at V08.

Table 3.2: Trial with 8 Visits, 5 Vaccinations, 5 Blood Samples, 7 Months Period/Subject

| Visit | V01 | V02 | V03 | V04 | V05 | V06 | V07 | V08 | | | |
|---|---|---------------|----------------|-------------------|-------------------|----------|------------------|----------|--|--|--|
| Visit interval | VAC1 | VAC2= VAC1+3D | VAC3 = VAC1+7D | VAC4 = VAC1+14D | VAC5= VAC1+28D | VAC5+14D | VAC5+28D | VAC5+6M | | | |
| Indicative Days (D)/ Months (M) | D0 | D3 | D7 ±1D | D14 ±1D | D28 ±3D | D42 ±3D | D56 ±3D | M7 ±14D | | | |
| Informed consent signed | √ | | | | | | | | | | |
| Demography | √ | | | | | | | | | | |
| Urine pregnancy test* | √ | √ | √ | √ | √ | | | | | | |
| Physical examination | √ | √ | √ | √ | √ | √ | √ | | | | |
| Past and current significant medical history | √ | | | | | | | | | | |
| Inclusion & exclusion criteria | √ | | | | | | | | | | |
| Randomization | √ | | | | | | | | | | |
| Blood sampling for serology (5 mL) | √ | | | √ | √ | √ | | √ | | | |
| Vaccine injection | √ | √ | √ | √ | √ | | | | | | |
| HRIG administration | √ | | | | | | | | | | |
| 30-minute observation period | √ | √ | √ | √ | √ | | | | | | |
| Diary Card (DC) Memory Aid (MA) Provided: Checked: Collected: | DC1 | DC1 | DC1 | DC2 DC1 DC1 | DC3 DC2 DC2 | DC3 | MA DC3 DC3 | MA MA | | | |
| Injection site reactions and Systemic Event Assessment | √ | √ | √ | √ | √ | √ | √ | | | | |
| Temporary contraindications | | √ | √ | √ | √ | | | | | | |
| Reportable concomitant medication | √ | √ | √ | √ | √ | √ | √ | | | | |
| Termination Record | | | | | | | | √ | | | |
| Definitive contraindications | Collected throughout the trial or up to V05 | | | | | | | | | | |
| Pregnancy cases | Collected throughout the trial | | | | | | | | | | |
| SAEs and AESIs | Collected throughout the trial | | | | | | | | | | |

* For subjects of childbearing potential

4 Endpoints and Assessment Methods

4.1 Immunogenicity Endpoints and Assessment Methods

See Section 9.1 of the protocol.

4.2 Safety Endpoints and Assessment Methods

See Section 9.2 of the protocol.

4.3 Derived Endpoints: Calculation Methods

4.3.1 Safety

Terms used in the standard safety tables to describe the safety events are specified below.

- AE: Adverse event includes immediate, solicited, and unsolicited non-serious, or serious event
- AR: Adverse reaction corresponds to related AE
- Immediate: Unsolicited systemic non-serious AE ticked “immediate (within 30 minutes from the vaccination)” by the investigator in the electronic case report form (eCRF) or SAE with time of onset within 30 minutes
- Solicited reaction: Event pre-listed in the eCRF, and which occurred during the solicited period
- Unsolicited AE: AE recorded in the eCRF as unsolicited or SAE forms, excluding solicited reaction. Therefore, include immediate AE.

Unsolicited non-serious injection site reactions are always recorded without relationship and analyzed as ARs.

Unsolicited AEs analyzed are AEs up to 28 days +3 days after vaccination. Unsolicited AEs occurring after the defined period - and which are not SAEs - will be presented in a separate listing.

- SAE: Unsolicited AE considered serious by the investigator (reconciled with Global Pharmacovigilance database)
- Adverse event of specific interest (AESI): the list of Medical Dictionary for Regulatory Activities (MedDRA) preferred terms (PT) defined in the protocol to select these AEs in the database:
 - Anaphylactic reaction (PT)
 - Encephalitis (PT)

- Convulsion (PT)

4.3.1.1 **Solicited Reactions**

4.3.1.1.1 **Daily Intensity**

All daily records for solicited reactions will be derived into daily intensity according to the following classification: None, Grade 1, Grade 2, Grade 3, or Missing.

For the derivation of daily intensities the following sequential steps will be applied:

1) For solicited reactions (except for fever) with an Investigator presence recorded as "No" and with all daily records missing, all daily intensities will be derived as "None."

2) For non-measurable solicited reactions, daily intensities will correspond to daily records reported in the clinical database. For measurable solicited reactions the daily measurements reported in the clinical database will be converted based upon the intensity scales defined in the protocol; this assumes a reaction that is too large to measure (not measurable [NM]) is Grade 3. Note the intensity could be considered "None" (not a reaction) in the analysis despite being considered a reaction by the investigator (e.g., swelling measurement > 0 mm but < 25 mm in adults).

Note: The maximum intensity on the ongoing period is derived from the record of the maximum intensity/measurement after the end of the solicited period following the rule described above.

4.3.1.1.2 **Maximum Overall Intensity**

Maximum overall intensity is derived from the daily intensities computed as described in Section 4.3.1.1.1 and is calculated as the maximum of the daily intensities over the period considered.

4.3.1.1.3 **Presence**

Presence is derived from the maximum intensity on the period considered:

- None: no presence
- Grade 1, Grade 2, or Grade 3: presence
- Missing: missing presence

Subjects with at least one non-missing presence for a specific endpoint will be included in the analysis. Conversely, those subjects without non-missing presence will not be included in the analysis of the endpoint.

4.3.1.1.4 **Time of onset**

Time of onset is derived from the daily intensities computed as described in Section 4.3.1.1.1. It corresponds to the first day with intensity of Grade 1, Grade 2, or Grade 3.

Note: If a reaction is not continuous (i.e., reaction occurs over two separate periods of time intervened by at least one daily intensity Missing or None) then the time of onset is the first day of the first occurrence.

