All noxious and unintended responses to a medicinal product related to any dose should be considered adverse reactions (AR).

(The phrase “responses to a medicinal product” means that a causal relationship between a medicinal product and an AE is at least a reasonable possibility)

Unexpected Adverse Reaction (UAR):

An unexpected adverse reaction is an AR, the nature or severity of which is not consistent with the applicable product information (e.g., Investigator's Brochure for an unapproved investigational medicinal product).

^a The term “life-threatening” refers to an event in which the subject was at risk of death at the time of the event; it does not refer to an event which hypothetically might have caused death if it were more severe.

^b All medical events leading to hospitalizations will be recorded and reported as Serious Adverse Events, with the exception of: hospitalization planned before inclusion into the study or out-patient treatment with no hospitalization.

^c “Persistent or significant disability or incapacity” means that there is a substantial disruption of a person’s ability to carry out normal life functions.

^d Medical and scientific judgment should be exercised in deciding whether expedited reporting is appropriate in other situations, such as important medical events that may not be immediately life-threatening or result in death or hospitalization but may jeopardize the health of the subject or may require intervention to prevent one of the other outcomes listed in the definition above. These should also usually be considered serious. Examples of such events include allergic bronchospasm requiring intensive treatment in an emergency room or at home, blood dyscrasias or convulsions that do not result in inpatient hospitalization, or the development of drug dependency or drug abuse, new onset diabetes, or autoimmune disease.

The following additional definitions are used by Sanofi Pasteur:

Solicited Reaction:

A solicited reaction is an event that is prelisted in the CRF. The assessment of these AEs post-vaccination is mandatory. A solicited reaction is defined by a combination of:

- Symptom and
- Onset post-vaccination

e.g., injection site pain between D0 and D03 post-vaccination, or headache between D0 and D07 after the last vaccination.

A solicited reaction is therefore an AR observed and reported under the conditions (symptom and onset) prelisted (i.e., solicited) in the CRF and considered as related to vaccination.

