9.2.3.2 Reactogenicity (Solicited Reactions From Day 0 to Day 7 After Each Vaccination)

After each vaccination, subjects will be provided with a safety diary card, a digital thermometer, and a flexible ruler, and will be instructed how to use them. The following items will be recorded by the subjects in the diary card on the day of vaccination and for the next 7 days^a (i.e., D0 to D7) until resolution:

- Daily temperature, with the route by which it was taken
- Daily measurement or intensity grade of all other solicited injection site and systemic reactions
- Action taken for each event, if any (e.g., medication)

For solicited reactions still ongoing after the solicited period, daily intensity will be recorded in the DC until resolution of the reaction.

The action taken by the subject to treat any **solicited reactions** will be classified in the CRF using the following scale:

- 0: None
- 1: Medication (self-medication with an existing prescription or over-the-counter medication)
- 2: Health care provider contact (no new medication prescribed)
- 3: Health care provider contact and prescription of a new medication (health care provider instructed subject to take a new medication, either an over-the-counter medication or one requiring a written prescription)
- 4: Hospitalization (inpatient)

[Table 9.1](#) and [Table 9.2](#) present, respectively, the injection site reactions and systemic reactions that are prelisted in the diary cards and CRF, together with the intensity scales.

^a As applicable

Table 9.1: Solicited injection site reactions: terminology, definitions, and intensity scales

CRF term (MedDRA lowest level term [LLT])	Injection site pain	Injection site erythema	Injection site swelling
Diary card (DC) term	Pain	Redness	Swelling
Definition		Presence of a redness including the approximate point of needle entry	Swelling at or near the injection site Swelling or edema is caused by a fluid infiltration in tissue or cavity and, depending on the space available for the fluid to disperse, swelling may be either soft (typically) or firm (less typical) to touch and thus can be best described by looking at the size of the swelling
Intensity scale*	Grade 1: No interference with activity Grade 2: Some interference with activity Grade 3: Significant; prevents daily activity	Grade 1: ≥ 25 to ≤ 50 mm Grade 2: ≥ 51 to ≤ 100 mm Grade 3: > 100 mm	Grade 1: ≥ 25 to ≤ 50 mm Grade 2: ≥ 51 to ≤ 100 mm Grade 3: > 100 mm

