4.3.1.2.4 Time of onset

Time of onset is derived from the start date of the unsolicited non-serious AE provided in the clinical database and the date of last vaccination:

- start date of the unsolicited non-serious AE – date of previous vaccination

The time of onset should be considered as missing only if one or both of the dates are missing or partially missing.

An AE with missing time of onset will be considered to have occurred just after the vaccination indicated by the visit number, so will be included in these tables. Note: Unsolicited non-serious AE that occurred before vaccination (negative time of onset) will not be included in analysis, but will be listed separately.

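### As written, the SAP counts a headache, malaise or myalgia still running at the next injection again as a new reaction to that next dose

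*SAP*

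**What the plan says.** **Definition.** Protocol 9.2.1 introduces the term with "A solicited reaction is defined by a combination of" and then lists symptom and onset after vaccination. It repeats that such a reaction is one "observed and reported under the conditions (symptom and onset) prelisted (i.e., solicited) in the CRF". SAP 4.3.1 uses a looser form: "Event pre-listed in the eCRF, and which occurred during the solicited period".

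**Derivation.** In SAP 4.3.1.1.3, "Presence is derived from the maximum intensity on the period considered", so any Grade 1 to 3 day in the window makes the reaction present. On time of onset, SAP 4.3.1.1.4 says: "It corresponds to the first day with intensity of Grade 1, Grade 2, or Grade 3". Neither rule looks at the subject's state before the injection.

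**Windows.** Injections fall on D0, D3, D7, D14 and D28. SAP 5.1.2.2.1 runs the systemic windows from dose 1 to dose 2, from dose 2 to dose 3, and then for 7 days after each later dose. Tables 5.2 and 5.3 give post-dose 1 onset days D0-D3 with up to 4 days of occurrence, and post-dose 2 onset days D0-D4 with up to 5. Read this way, the injection day belongs to two windows.

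**Recording.** Under protocol 9.2.3.2 subjects grade every solicited reaction daily from the day of vaccination, and "For solicited reactions still ongoing after the solicited period, daily intensity will be recorded in the DC until resolution of the reaction".

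**Unsolicited events.** SAP 4.3.1.2.3 assigns each event to one vaccination, and SAP 4.3.1.2.4 states: "Unsolicited non-serious AE that occurred before vaccination (negative time of onset) will not be included in analysis". Solicited reactions have no matching step.

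**The concern.** The safety objective is the profile after each injection, and the choice of VRVg-2 dosage draws on it. If one continuing symptom is scored under two or three doses, the systemic rates for doses 2 and 3 mix new reactions with carry-over from the dose before. A group with more frequent or longer reactions to dose 1 would then also look more reactogenic after doses 2 and 3 without any new reaction. One difference between dosages would be repeated across several rows of the table and could be read as independent confirmation.

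**Working it through.** **1. The rules applied to diary records** (injections on D0, D3, D7, D14, D28; systemic windows D0-D3, D0-D4, D0-D7, D0-D7, D0-D7 after doses 1 to 5)

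| Graded study days | Scored under |
|---|---|
| Headache D2-D5 | dose 1 (onset D2, 2 days) and dose 2 (onset D0, 3 days) |
| Headache D1-D7 | dose 1 (onset D1), dose 2 (onset D0) and dose 3 (onset D0) |
| Myalgia D12-D15 | dose 3 (onset D5) and dose 4 (onset D0) |
| Any symptom on D3 only | dose 1 (D3) and dose 2 (D0) |

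In the first row a 4-day reaction yields 2 + 3 = 5 dose-level days. Assigning the injection day to one window does not cure it. With D3 given to dose 2, D2 remains under dose 1 and D3-D5 fall under dose 2. With D3 given to dose 1, D4-D5 still fall under dose 2.

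**2. Does another SAP rule remove the second count?** SAP 4.3.1.1.6 (overall days) and 4.3.1.1.7 (ongoing) extend a reaction under the earlier dose. Neither takes it out of the next dose's window.

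**3. Possible size.** The plan has no figure for carry-over. For scale, the Clopper-Pearson intervals in SAP Table 5.5 were recomputed and all five agree to one decimal (for example 12/80: 8.0 to 24.7).

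Assumptions, none from the documents: systemic rate after dose 1 p1 = 30%; new-onset rate after later doses p2 = 15% or 20%; onset 0, 1 or 2 days after the dose with probability 0.50, 0.35, 0.15; geometric duration with mean m; doses independent. The shared injection day is not used for carry-over.

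Let q = 1 - 1/m. A dose-1 reaction is still graded on D4, the day after dose 2, with probability

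c = 0.50q⁴ + 0.35q³ + 0.15q²

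Counted dose-2 rate = 1 - (1 - p2)(1 - c × p1)

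| Mean duration m | c | p2 = 15% becomes | p2 = 20% becomes |
|---|---|---|---|
| 1.5 days | 0.036 | 15.9% (+6%) | 20.9% (+4%) |
| 2 days | 0.113 | 17.9% (+19%) | 22.7% (+14%) |
| 2.5 days | 0.194 | 20.0% (+33%) | 24.7% (+23%) |
| 3 days | 0.269 | 21.9% (+46%) | 26.5% (+32%) |

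Percentages in brackets are relative. Simulation under the same assumptions agrees to within about a point and gives +1% to +24% for dose 3, 0 to +6% for dose 4 and about 0 for dose 5.

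**4. Between-group effect.** Take two groups of 80 with the same true dose-2 rate of 15%, dose-1 rates of 30% and 20%, and equal durations. The spurious difference is 0.85 × (0.30 - 0.20) × c, which is 0.3, 1.0, 1.7 and 2.3 percentage points for the four durations. At the largest, 80 × 0.023 is fewer than 2 subjects. If durations also differ (3 days against 2), it is 0.85 × (0.30 × 0.269 - 0.20 × 0.1125) = 5.0 points, or 4 subjects.

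**The case against.** The strongest reply is that the SAP grades daily records in the clinical database, not the raw diary. Records reach the database after an interview and transcription, and the site also enters an investigator presence field. Protocol 9.2.1 ties the onset condition to the CRF, and SAP 4.2 adopts protocol 9.2 by reference. If sites enter a running reaction only under the earlier dose, using its ongoing period and stop date, no double count arises. The protocol's instruction to grade until resolution fits that mechanism. This stands as a possibility: the eCRF layout and completion guidelines are not in the documents, but nothing provided gives that instruction.

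Several stronger readings are tempting and are not supported:

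- **That the SAP deliberately abandons the onset condition.** It refers to the protocol's section, so the fault is a derivation that does not implement the definition.
- **That onset tables are badly distorted.** Table 5.2 groups systemic onset after dose 2 as D0-D3 or D4, so a shift to D0 hardly shows.
- **That durations are wrong.** SAP 4.3.1.1.5 counts graded days over the period considered, as it says, and 4.3.1.1.6 gives overall days separately.
- **That fever is affected like the rest.** Protocol 5.2.7.1 postpones vaccination for febrile illness, which largely blocks carried-over fever. The same section covers moderate or severe acute illness.
- **That the dosage choice is undermined.** Protocol section 12 names the RVNA proportion, GMTs and titer distribution in particular, no hypothesis is tested, and the likely between-group distortion is small against the planned intervals.

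**Conclusion.** The point holds on the written rules. A solicited headache, malaise or myalgia still present at the next injection is scored again for that dose, with onset D0, and no SAP step prevents it. The effect is confined to per-dose systemic rates, chiefly after doses 2 and 3 and slightly after dose 4. Occurrence after any injection is unchanged, because each subject counts once.

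The size cannot be fixed from the documents. The 4% to 46% relative rise at dose 2 depends wholly on assumed rates, onset pattern and durations, and its upper end belongs to the longest duration tried. The between-group distortion is probably only a few percentage points, reaching about 5 only when both frequency and duration differ between groups. A reader might infer that the dosage comparison is seriously biased. The documents do not support that, both because of this size and because the eCRF may already keep running reactions under the earlier dose. It remains worth correcting, because the per-dose profile is the stated safety objective.

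**What to change.** In SAP 4.3.1.1.3 and 4.3.1.1.4:

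1. State which dose's window owns the injection day, so that no diary day counts for two doses.
2. For doses 2 to 4, report two per-dose rows for solicited systemic reactions. The new-onset row counts a reaction with no Grade 1 to 3 on the last diary day before the injection, or one that recurs after a day recorded None or Missing, which is the SAP's own test of continuity. The all-occurrence row keeps the present rule. Show reactions continuing from the earlier dose separately and flag any rise in grade.
3. Align the definition in SAP 4.3.1 with the protocol's onset condition.

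The cost is SAP wording and a few lines of programming on daily intensities already collected. The downside is that a symptom continuing at the same grade because of the new dose is missing from the new-onset row. Attribution of a continuing symptom is a convention, so both rows should be shown.

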4.3.1.1.5 Number of Days of Occurrence

Number of days of occurrence over the period considered is derived from the daily intensities computed as described in Section 4.3.1.1.1. It corresponds to the number of days with daily intensities of Grade 1, Grade 2, or Grade 3. Number of days of occurrence on the solicited period with a specified intensity may also be derived.

4.3.1.1.6 Overall Number of Days of Occurrence

If a reaction is ongoing at the end of the solicited period, then the overall number of days of occurrence is derived from the daily intensities and the stop date of the reaction after the end of the solicited period. The overall number of days of occurrence is:

- (stop date – last vaccination date) + (number of days of occurrence within the solicited period) – length of the solicited period + 1

If the stop date is missing or incomplete (contains missing data [MD]), the overall number of days of occurrence will be considered as “Missing”.

4.3.1.1.7 Ongoing

Ongoing is derived from the last daily intensity of the solicited period computed and the maximum intensity on the ongoing period. The investigator’s ongoing flag is not used because the measurement would determine the ongoing status of the reaction. Note the intensity could be considered None (not a reaction) in the analysis despite being considered a reaction by the investigator (e.g., swelling measurement > 0 mm but < 25 mm in adults). If the last daily intensity of the solicited period is at least Grade 1 and maximum intensity on the ongoing period is also at least Grade 1, then the reaction is considered “ongoing”. In any other cases the reaction will not be considered as “ongoing”.

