|-----------------|--|----------------|
| Post-dose 3,4,5 | | D0-D3 D4-D7 |
|-----------------|--|----------------|

- Range of number of days of occurrence categories are in Table 5.3

Table 5.3: Range of Number of Days of Occurrence Categories for Solicited Reactions during the solicited period

| | Injection Site Reactions | Systemic Reactions |
|------------------|------------------------------------|--------------------------|
| Post-dose 1 | 1 - 3 days 4 - 7 days 8 days | 1 - 3 days 4 days |
| Post-dose 2 | | 1 - 3 days 4 - 5 days |
| Post-dose 3, 4,5 | | 1 - 3 days 4 - 7 days |

Solicited reaction after any injection

“After any injection” means after the five scheduled vaccine injections, and at least after the first vaccine injection (D0).

The solicited reaction will be presented after any injections according to:

- Overall occurrence over the D0-D7 period for injection site reactions or between vaccinations for systemic reactions (up to D7 for the last 2 vaccinations)
- Time of onset period
- Intensity grade: the maximum intensity grade will be computed during the solicited period for all solicited reactions and overall for on-going solicited reactions.

30-minutes Post-Vaccination Observation Period

Unsolicited systemic AEs occurring within 30 minutes after each vaccination will be presented in summary safety tables, analyzed according to their nature (SOC and PT of the MedDRA classification) and will be listed.

Unsolicited Adverse Events

The unsolicited non-serious AEs will be analyzed

- “Between the first and the second vaccine injection”, which corresponds to AEs reported at V02 and occurring after the first vaccine injection †

† For subjects interrupting their vaccination schedule after the first injection, unsolicited AEs until 28 days after the first injection are collected at visit V02

- “Between the second and the third vaccine injection”, which corresponds to AEs reported at V03 and occurring after the second vaccine injection [†]
- “Between the third and the fourth vaccine injection”, which corresponds to AEs reported at V04 and occurring after the third vaccine injection [§]
- “Between the fourth and the fifth vaccine injection”, which corresponds to AEs reported at V05 and occurring after the fourth vaccine injection ^{**}
- “Within 28 days after the fifth vaccine injection”, which corresponds to AEs reported at V07 and occurring after the fifth vaccine injection

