5.3.2.4 Intensity

For solicited reactions, missing intensities will be handled as described in Section 4.3.1.1.1.

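### A blank last diary day makes a persisting solicited reaction not ongoing, so its recorded post-window grade drops out of the overall maximum intensity

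*SAP*

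**What the plan says.** The status rule in SAP 4.3.1.1.7 has two conditions, both required: "If the last daily intensity of the solicited period is at least Grade 1 and maximum intensity on the ongoing period", with the second also having to reach Grade 1. For everything else, "In any other cases the reaction will not be considered as" ongoing. The investigator's "ongoing flag is not used because the measurement would determine the ongoing status of the reaction".

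Under SAP 4.3.1.1.1, daily records "will be derived into daily intensity according to the following classification: None, Grade 1, Grade 2, Grade 3, or Missing". The only fill-in rule there concerns a reaction, other than fever, that the investigator marked as absent "and with all daily records missing, all daily intensities will be derived as" None. SAP 5.3.2.4 adds nothing further: "For solicited reactions, missing intensities will be handled as described in Section 4.3.1.1.1". SAP 5.3.2 plans no replacement of missing safety data.

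The status controls two results. For intensity, SAP 5.1.2.2.1 states that "the maximum intensity grade will be computed during the solicited period for all solicited reactions and overall for on-going solicited reactions". For duration, SAP 4.3.1.1.6 derives the overall number of days only when the reaction is ongoing at the end of the solicited period.

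The post-window data exist. Protocol 9.2.3.2: "For solicited reactions still ongoing after the solicited period, daily intensity will be recorded in the DC until resolution of the reaction". SAP 4.3.1.1.1 takes the maximum on the ongoing period from that record.

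**The concern.** A missing value is being handled as if it were a recorded None. If the last day is blank, a reaction graded the day before and graded again after the window fails the first condition and falls into the default class.

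The reason given for ignoring the investigator's flag does not reach this case. It concerns reactions that the investigator calls present but whose measurement is too small to count, such as swelling under 25 mm. That supports the rule for a last day of None. It says nothing about a blank day, and it has no bearing on pain, headache, malaise or myalgia, which are not measured.

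Elsewhere the SAP leans the other way. Missing causality counts as related (5.3.2.2), unsolicited events with a missing time of onset stay in the analysis (5.3.2.5), and denominators are chosen so that incidences are not understated (5.1.2.2.1).

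Protocol section 12 bases the choice of dosage partly on the descriptive safety profiles of the three VRVg-2 groups. In groups of 80, a single Grade 3 reaction shown at a lower grade is visible in a table.

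**Working it through.** The plan gives no figure to reproduce, so the check traces the derivation.

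**Step 1: a blank last day.** The daily intensity is Missing. The fill-in rule does not apply, because it needs every daily record missing and the reaction marked absent. Missing is not at least Grade 1, so the first condition fails and the reaction is not ongoing, whatever the post-window record shows.

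**Step 2: a worked case (assumed data).** Injection-site pain, window D0 to D7 (8 days), Grade 2 on D4 to D6, post-window maximum Grade 3, stop on D12. The SAP 4.3.1.1.6 formula is (stop date − vaccination date) + in-window days − window length + 1.

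| D7 record | In-window days | In-window maximum | Ongoing | Overall maximum | Overall days |
|---|---|---|---|---|---|
| Grade 2 | 4 | Grade 2 | yes | Grade 3 | 12 + 4 − 8 + 1 = 9 |
| Missing, rule as written | 3 | Grade 2 | no | Grade 2 (in-window only) | not derived |
| Missing, last recorded day used | 3 | Grade 2 | yes | Grade 3 | 12 + 3 − 8 + 1 = 8 |

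If the post-window maximum were Grade 2 or lower, the maximum would be Grade 2 in all three rows. Only the status and the overall days would then differ.

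**Step 3: shorter systemic windows (assumed data).** The rule behaves the same way.
- Post-dose 1, D0 to D3 (4 days): Grade 1 from D1, post-window Grade 2, stop D6. With D3 graded: ongoing, Grade 2, 6 + 3 − 4 + 1 = 6 days. With D3 blank: not ongoing, Grade 1, no overall days.
- Post-dose 2, D0 to D4 (5 days): Grade 1 from D2, post-window Grade 2, stop D8. With D4 graded: ongoing, Grade 2, 8 + 3 − 5 + 1 = 7 days. With D4 blank: not ongoing, Grade 1, no overall days.

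**Step 4: which outputs change.** Overall maximum intensity is planned after each injection and after any injection, so that loss reaches tables. SAP Table 5.3 counts only days inside the solicited period, so the worked case with D7 blank shows 3 days there whatever its status. SAP 5.1.2.2.1 lists no table of the overall number of days.

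**Step 5: which reactions are exposed.** With injections at D0, D3, D7, D14 and D28, the systemic windows run about D0–D3, D3–D7, D7–D14, D14–D21 and D28–D35. The first three end where the next begins, so a systemic reaction persisting after injections 1 to 3 can be graded in the next window and reach the after-any-injection maximum. After injections 4 and 5 no window follows directly. For injection-site reactions the next injection is on the opposite side (Protocol 5.1.4), so its record concerns another site.

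**Step 6: frequency.** The documents give neither the number of persisting reactions nor the blank rate. As an assumption only, take 4 to 16 persisting reactions per group of 80 and 1% to 10% blank last days, unrelated to persistence. Expected status changes per group run from 4 × 0.01 = 0.04 to 16 × 0.10 = 1.6. The chance of at least one runs from 1 − 0.99^4 = 4% to 1 − 0.90^16 = 82%. These count changed statuses; changed maximum grades are a subset.

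**The case against.** The best defence is that the case should be rare and the convention is coherent. Protocol 11.1 has the investigator or a designee interview subjects and try to clarify incomplete diary entries, and Protocol 13.2 has the coordinator obtain verbal clarification of missing diary data. The SAP expects little missing safety data. SAP 4.3.1.1.4 already lets a Missing day separate two periods of a reaction, just as None does. The rule is the same in every group, and no hypothesis is tested.

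Much of this stands, and it limits the size. The parallel with 4.3.1.1.4 is weaker than it looks: there, a Missing day merely leaves the onset at the first occurrence, whereas in 4.3.1.1.7 it removes a recorded grade from a planned summary.

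One might also read the last daily intensity as the last non-missing one, which would resolve the case. The SAP does not say so, and Missing is itself a derived value.

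Three stronger readings are tempting but unsupported:
- A reader might infer that the tables would report 3 days instead of 8 in the worked case. They would not: the planned display is confined to in-window days, and the overall number of days is simply not derived.
- A reader might infer that maximum intensity is always understated. It is understated only when the post-window grade exceeds the in-window maximum.
- A reader might infer that every blank last day followed by a post-window grade should count as ongoing. That would also take in reactions whose last recorded day was None, or that had no graded day in the window.

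**Conclusion.** The point holds as a defect in a stated rule. When the last daily intensity is Missing, SAP 4.3.1.1.7 classes a reaction as not ongoing even though its last recorded in-window day was graded and a post-window grade of at least Grade 1 is on file. The overall maximum can then only be too low or unchanged, never too high, and the overall number of days is left underived.

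The scope is narrow: mainly injection-site reactions and systemic reactions after injections 4 and 5. The effect is probably small, given the diary queries, and its frequency cannot be derived from the documents. The conclusion rests on reading the last daily intensity as that of the final day of the window. If the last non-missing day was meant, the same sentence is still needed to say so.

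**What to change.** In SAP 4.3.1.1.7, state that if the last daily intensity of the solicited period is Missing, the last non-missing daily intensity of that period is used for the status test. If that intensity and the maximum on the ongoing period are both at least Grade 1, the reaction is ongoing. The rule for a last daily intensity of None stays.

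The cost is one SAP sentence and one programming condition, on data already collected. No grade is imputed and the blank day is not counted, which is why the worked case gives 8 overall days rather than 9.

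The downside is that a Missing day would still separate periods for time of onset in 4.3.1.1.4 but would no longer end a reaction for ongoing status. The SAP should note that difference.
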